Action for Health in Diabetes (Look AHEAD, 2000-2012) was a 2-arm randomized, controlled multicenter clinical trial to examine whether an intensive lifestyle intervention (ILI) designed to achieve and maintain weight loss of at least 7% by focusing on reduced caloric intake and increased physical activity could reduce cardiovascular morbidity and mortality compared with Diabetes Support and Education (DSE), a standard care control group. Look AHEAD enrolled 5,145 overweight or obese volunteers with type 2 diabetes, with a planned follow-up period of up to 13.5 years. At randomization, the Look AHEAD cohort was comprised of 60% females, 37% minorities, mean age of 59.7 years (range: 45-76 years), and mean BMI of 35.9 kg/m²; the mean duration of diabetes was 5 years and 14% had a prior history of CVD at baseline. The primary endpoint was the first occurrence of a composite cardiovascular outcome that included death from cardiovascular causes, nonfatal myocardial infarction, nonfatal stroke, and hospitalized angina with a targeted between-group difference of 18% reduction in the composite endpoint in ILI vs. DSE. Three composite cardiovascular outcomes were also examined: 1) death from cardiovascular causes, nonfatal myocardial infarction, or nonfatal stroke; 2) death from any cause, myocardial infarction, stroke, or hospitalization for angina; and 3) death from any cause, myocardial infarction, stroke,

[figure not shown]

coronary-artery bypass grafting, percutaneous coronary intervention, hospitalization for heart failure, or peripheral vascular disease.

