1.4.2 Secondary Outcomes

The secondary outcomes are: 1) frailty, 2) diabetic microvascular complications, and 3) quality of life.

Frailty will be assessed using the Fried criteria (Fried, 2001), which is based on the presence of five frailty characteristics: (1) walking speed standardized based on median height and sex, (2) grip strength standardized based on body mass index (BMI) and sex, (3) energy expenditure standardized based on sex, (4) exhaustion based on self-report, and (5) weight loss of 10 lbs. or more in the last year without intention. Walking speed will be assessed using the timed short walk included in the Short Physical Performance Battery (SPPB). Grip strength will be measured twice in each hand to the nearest 2 kg using an isometric Hydraulic Hand Dynamometer (Jamar, Bolingbrook, IL), and the value from the stronger hand will be used. Participants will be excluded if they report hand pain or recent hand or wrist surgery. Energy expenditure will be based on kcal/week of energy derived from the Paffenbarger Physical Activity questionnaire (Paffenbarger 1978), a short instrument designed to measure participation in leisure time physical activity. Exhaustion will be assessed using the PHQ-9 question: “During the past two weeks, how often have you been bothered by feeling tired or having little energy – not at all, several days, more than half of the days, nearly every day?” Weight loss will be assessed by self-report (we acknowledge that this is a difficult item to interpret for the Look AHEAD cohort, and will also examine the impact on a construct without this item). Based on these assessments, frailty will be classified into three stages: non-frail (no frailty characteristics present), pre-frail (1 or 2 frailty characteristics present), and frail (3 or more frailty characteristics present).

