Frailty is the primary outcome for this aim and is a new aim because it has not been measured prior to LA-E. It will be assessed using the Fried criteria [Fried, 2001] developed during the Cardiovascular Health Study. Frailty classification is based on the presence of five frailty characteristics: 1) walking speed standardized based on median height and sex, 2) grip strength standardized based on body mass index (BMI) and sex, 3) energy expenditure standardized based on sex, 4) exhaustion based on self-report, and 5) weight loss of 10 lbs or more in the last year without trying or intending to (based on self-report). Walking speed will be assessed using the timed short walk included in the Short Physical Performance Battery (SPPB) and grip strength. Energy expenditure will be based on kcal/week of energy derived from the Paffenbarger physical activity questionnaire. Exhaustion will be assessed using the question from the Geriatric Depression Scale, "Do you feel full of energy?." Weight loss will be assessed by self-report. (We acknowledge that this is a difficult item to interpret for the LA cohort, and will also examine the impact on a construct without this item.) Based on these assessments, frailty will be classified into three stages: non-frail (no frailty characteristics present), pre-frail (1 or 2 frailty characteristics present), and frail (3 or more frailty characteristics present). Our primary analysis will classify a person as having prevalent frailty if they are classified as frail during either of the LA-E visits. The proportion of participants experiencing any frailty will be compared between randomized groups using logistic regression, with clinic site, sex, and time from randomization to classification of frailty or the last non-frail classification as covariates. Odds ratios and 95% confidence intervals will be used to summarize the relative effect of the intervention on frailty.

Supporting analyses: include persistent major mobility disability (PMMD) based on repeated assessments of the adjudicated 400-m walk, sensitivity analyses for frailty and PMMD, falls, fractures, SPPB, grip strength, and Pepper Assessment Tool for Disability (PAT-D).

PMMD is considered present when an individual fails to complete two successive 400-m walks [Newman, 2006; Pahor, 2014]. Death after an initial MMD determination will also be considered

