PMMD. Additionally, information used in the adjudication of MMD (i.e. self- or proxy report of inability to walk across a small room without the assistance of another person) in the absence of 400-m walk data will be collected every 6-months via telephone and will be used to ascertain PMMD. We will define PMMD based on the sequence of 400-m walks from LA-C (one) and LA-E (twice). In addition, those who failed the 400-m walk for the first time at their last scheduled LA-E clinic visit and who are not adjudicated as persistent failures will return 6 months later for a repeat assessment to establish persistence. The proportion of participants experiencing any PMMD will be compared using logistic regression models. The basic model will include an indicator variable for intervention assignment, follow-up time with covariate adjustment for sex and clinical site. Follow-up time for PMMD will be considered as the time until the initial MMD failure or last successful completion of the 400-m walk for those without PMMD. Odds ratios and 95%CI will be used to summarize the relative effect of the intervention on PMMD.

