SPPB was developed to measure lower-extremity physical function as reflected in balance, gait speed, strength and endurance; and is comprised of the ability to stand with feet together in the side-by-side, semi-tandem, and tandem positions, time to walk 8-feet, and time to rise from a chair and return to the seated position 5 times [Guralnik, 1993]. The SPPB was modestly expanded to minimize ceiling effects of the SPPB when used in younger, more well-functioning populations: the holding time of the standing balance tasks was increased to 30 seconds and a single leg stand added [Simonsick, 2001]. The component scores on the expanded SPPB are calculated as the ratio of observed performance to the best possible performance and summed to provide a continuous total score. In addition, **grip strength** will be measured twice in each hand to the nearest 2 kg using an isometric Hydraulic Hand Dynamometer (Jamar, Bolingbrook, IL), and the value from the stronger hand will be used. An additional analysis of physical function will be performed from the 19-item version of the **Pepper Assessment Tool for Disability (PAT-D)**. The overall PAT-D score will be the mean of the 19 items. Disability scores from the 3 subscales will also be calculated: the basic Activities of Daily Living (ADL) with 7 items, the mobility disability score with 8 items, and the instrumental ADL score with 6 items.

All these physical function measures were collected once during LA-C and will be measured twice in LA-E. The average post-intervention difference between DSE and ILI will be compared using linear mixed effects models. The basic model will include an indicator variable for intervention assignment, a follow-up time effect (3 levels), and the interaction between the intervention and follow-up time while adjusting for clinic centers. The covariance between repeated measures will be characterized with an unstructured covariance structure and a linear contrast will be used to test for the significance of the overall intervention effect across follow-up.

Subgroup analyses: Pre-specified subgroup comparisons include sex, history of cardiovascular disease, race/ethnicity, and age. We will report tests of interactions to assess the consistency of differences between intervention groups for each of these subgroups.

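### SAP 5.3 leaves sex and age out of the mixed models for grip strength, SPPB and PAT-D; the comparison is valid but loses precision, mainly for grip strength

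*Combined protocol and SAP*

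**What the plan says.** Protocol 1.4.2 and SAP 5.3 use sex when frailty is scored. The grip item, for example, is "grip strength standardized based on body mass index (BMI) and sex". The frailty logistic model in SAP 5.3 is fitted "with clinic site, sex, and time from randomization to classification of frailty or the last non-frail classification as covariates", and the model for persistent major mobility disability (PMMD) has "follow-up time with covariate adjustment for sex and clinical site".

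The continuous physical-function outcomes of the same aim are treated differently. For grip strength, "the value from the stronger hand will be used", and no standardisation is mentioned. For grip strength, expanded SPPB and PAT-D together, the SAP says: "All these physical function measures were collected once during LA-C and will be measured twice in LA-E". It then says: "The average post-intervention difference between DSE and ILI will be compared using linear mixed effects models". Besides the arm indicator, the basic model has "a follow-up time effect (3 levels), and the interaction between the intervention and follow-up time while adjusting for clinic centers". Neither sex nor age is in it. In SAP 5.3 both appear among the subgroup factors, which are to be tested as interactions.

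Protocol 1.1 describes the cohort at randomization as "comprised of 60% females, 37% minorities, mean age of 59.7 years (range: 45-76 years").

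**The concern.** In a linear model, a strong predictor of the outcome that is left out goes into the residual variance. Randomization keeps the arm comparison unbiased, but its standard error is larger than it need be. Raw grip strength is the outcome where this is most likely to matter. The plan itself treats sex as important enough to standardise grip for the frailty threshold and to adjust two binary models, yet omits it where raw kilograms are averaged across men and women.

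The usual remedy, adjusting for the outcome's own baseline value, is not available, because these measures were first taken in the Continuation study, after the intervention had ended. SAP 5.4 does adjust for a baseline value where one exists (eGFR and the MNSI questionnaire). For the Aim 3 measures, sex and age at randomization are the natural substitutes: both have been held since randomization, and ILI cannot affect either. What is at stake is the width of the confidence intervals for three supporting outcomes.

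**Working it through.** **Is there a stated figure to reproduce?** Not for these outcomes. The documents give no SD, power or detectable difference for grip strength, SPPB or PAT-D. The neighbouring Aim 3 figures confirm the basis of 1900 per arm, two-sided 0.05:

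- Frailty: 8% in DSE with an odds ratio of 0.70 gives 5.74% in ILI and 78.7% power (80% stated).
- PMMD: 12.7% with an odds ratio of 0.75 gives 9.84% and 79.7% power (about 80% stated).

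Both reproduce to within 2 percentage points. Neither concerns the outcomes at issue.

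**Reference comparison.** Take one visit, 1900 per arm, two-sided 0.05 and 80% power without sex in the model. The detectable difference is (1.96 + 0.84) × √(2/1900) = 2.80 × 0.0324 = 0.091 total SD. This 80% is a yardstick, not a claim made by the plan.

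**Adding sex.** Let p = 0.60 be the proportion female (Protocol 1.1, original cohort, assumed to hold among attendees). Let d be the male-female difference in within-sex SDs at a single visit, which is an assumption. Then:

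- R² = p(1−p)d² / (1 + p(1−p)d²), with p(1−p) = 0.24
- standard error multiplier = √(1−R²)
- equivalent sample size = 1/(1−R²)
- power at the same true difference = Φ(2.80/√(1−R²) − 1.96)

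| Assumed d | R² | SE multiplier | Equivalent extra participants | Detectable difference (total SD) | Power |
|---|---|---|---|---|---|
| 0.5 | 0.06 | 0.97 | 6% | 0.088 | 82% |
| 1.0 | 0.19 | 0.90 | 24% | 0.082 | 88% |
| 1.5 | 0.35 | 0.81 | 54% | 0.073 | 94% |
| 2.0 | 0.49 | 0.71 | 96% | 0.065 | 97.5% |

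Worked line for d = 1: 0.24/1.24 = 0.194; √0.806 = 0.898; 2.80/0.898 − 1.96 = 1.16; Φ(1.16) = 0.88.

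**Outcomes that sex and age predict weakly.** This may be the case for SPPB and PAT-D. The same formulas with R² assumed directly give:

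| Assumed R² | SE multiplier | Equivalent extra participants | Power |
|---|---|---|---|
| 0.02 | 0.99 | 2% | 81% |
| 0.10 | 0.95 | 11% | 84% |
| 0.20 | 0.89 | 25% | 88% |

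**Three visits instead of one.** Assume a within-sex variance of 0.75 between persons and 0.25 between visits, and an age effect of 0.25 within-sex SD per SD of age. Averaged over three visits, the adjusted variance is 0.75 + 0.25/3 = 0.833. The unadjusted variance adds 0.24d² + 0.0625. The standard error ratios for d = 1, 1.5 and 2 are then √(0.833/1.136) = 0.86, √(0.833/1.436) = 0.76 and √(0.833/1.856) = 0.67. A simulation of 1000 runs with 3800 participants gave 0.84, 0.78 and 0.68. In it, both estimators averaged within 0.002 of the true value of zero, so neither is biased.

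**The case against.** The case for leaving the model alone has several parts.

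- **Nothing in the plan is invalid, and no stated figure depends on it.** This stands. The outcomes are supporting analyses of a secondary aim, and SAP 5.3 gives power only for frailty and PMMD.
- **The size rests wholly on assumptions.** This stands too. The documents supply neither a sex difference nor an SD, and for age only a mean and a range.
- **The unadjusted comparison is already sensitive.** It can detect 0.091 total SD. Even at d = 2, where the total SD is √1.96 = 1.4 within-sex SDs, that is 0.127 within-sex SD against 0.091 adjusted. A reader might infer that a null grip result would merely reflect men and women being mixed in the error term. The figures do not support that: a null would mostly mean a small effect.
- **Sex-specific frailty scoring is a different matter.** It applies a published case definition. It is not a promise to adjust a continuous outcome, so the Protocol 1.4.2 sentence is not wrong. The closer comparison is with the frailty and PMMD models, which do carry sex.
- **Adjusting for clinic alone is a defensible convention.** SAP 5.2 says that randomization was stratified by clinic only. That makes the omission acceptable, but does not make it efficient.
- **The plan leaves room.** The model is called *basic*, sex and age are subgroup factors, and SAP 4.4 allows covariates in sensitivity analyses. None of these supplies an adjusted main effect. Interaction tests answer another question, and SAP 4.4 concerns predictors of missingness, with primary weight kept on the original analysis.

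A reader might also count chance sex imbalance between arms as a further harm. It is already contained in the unadjusted standard error, so it is the same loss seen from another side.

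**Conclusion.** The point holds as a loss of precision, at low priority. Sex and age at randomization are missing from the basic model for three continuous outcomes that have no pre-randomization value. For grip strength, an assumed sex difference of 0.5 to 2 within-sex SDs with 60% female means that sex explains about 6% to 49% of between-person variance. A single-visit comparison with 80% power would rise to about 82% to 98%. For SPPB and PAT-D the gain may be small: about 81% to 88% for an assumed R² of 0.02 to 0.20. The direction does not depend on these assumptions as long as the covariates predict the outcome, but the size depends on them entirely.

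Two extensions that a reader might draw are not supported:

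- **Baseline SF-36 physical functioning as a further covariate.** SAP 5.5 gives the administration schedule but does not show that a baseline score is held for everyone.
- **Age in the frailty and PMMD logistic models.** Odds ratios are non-collapsible, so adding age changes the conditional odds ratio being estimated, including for the aim's principal outcome, which SAP 5.3 powers at 0.70. No calculation supports that change.

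No stated power, sample size or primary conclusion is affected.

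**What to change.** In SAP 5.3, add one sentence to the basic linear mixed model for grip strength, expanded SPPB and PAT-D: sex and age at randomization enter as fixed covariates. Keep the clinic-only model as a sensitivity analysis. Do not add current BMI, even though the frailty grip item uses it, because it is measured after randomization and may be affected by ILI.

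The cost is two degrees of freedom (with age entered linearly) and no new data. Because the model is linear, the average arm difference being estimated is the same with and without the covariates. The change should be made before results by arm are seen, since choosing prognostic covariates afterwards would invite a charge of selection.

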1.4.3 Tertiary Outcomes

Tertiary outcomes include weight, physical activity, fat and lean mass, bone density, and cognitive function.

Their long-term trajectories will be described within and between intervention groups and their relationship to the primary and secondary outcomes will be examined.

Weight will be measured at the biennial clinic visits following the same standardized protocol that has been used throughout Look AHEAD.

Physical activity will be assessed by accelerometry. Physical activity and sleep data are obtained over a 24-hour period and are summarized in two ways: duration (time in minutes) and intensity of movement (threshold of activity count/min). Participants will be instructed to wear the accelerometer for a period of seven days, including one weekend day, for a period of 24 hours per day.

The sample size for this Look AHEAD Extension substudy will be approximately 1800 individuals currently active Look AHEAD -C and participated in the accelerometry sub studies in the past. The Central Reading Center for the accelerometry data will receive and process these data and transmit summary scores to the coordinating center.

In addition, all participants will complete the Paffenbarger Physical Activity Questionnaire (Paffenbarger 1978) to assess leisure time activity. This questionnaire was administered to the same subgroup described above at baseline, year 1 and year 4 , and to all Look AHEAD participants at year 8.

Fat and lean mass, bone density and bone mineral content will be assessed by DXA in a subset of 800 participants at five Look AHEAD sites (Baton Rouge, Boston-MGH, Houston, Los Angeles, and Seattle) who were part of the original Look AHEAD substudy examining these outcomes. The UCSF DXA QA Center was responsible for quality control during the original trial and will continue in this capacity for Look AHEAD Extension. Scans will be sent to the UCSF DXA QA Center for quality review of acquisition, and incorporation into a centralized database of DXA results. UCSF will provide a standard protocol to the densitometer sites, training in the specific study procedures for the DXA technicians, and certification of the technicians as qualified for Look AHEAD Extension scanning. DXA results will be provided to the participants. In addition, UCSF will notify the clinical site if a total hip, femoral neck or lumbar spine BMD T-score is below -2.5, and the clinical site will alert the participant. Quality control will include careful attention to machine cross calibration. Longitudinal changes in densitometer performance will be monitored using spine and whole body phantoms.

Cognitive assessment Among participants who consent, the 30-45 min cognitive battery used in the Look AHEAD Continuation (Rapp, 2017) will be repeated. It includes validated measures of attention and concentration, verbal learning and memory, processing speed, executive function, and global cognitive functioning,

Cognitive Impairment. Cognitive impairment (dementia and mild cognitive impairment) will be centrally adjudicated with the same protocol as used in the Look AHEAD Continuation (Espeland, 2017). Adjudication will be based on all available data for individuals whose scores on the Modified Mini Mental State Exam fall below age- and education-specific cut points. This triggers telephone administration of the Functional Assessment Questionnaire to a proxy, identified by the participant to query functional status in instrumental activities of daily living. Additional cases of cognitive impairment will be ascertained through interviews of proxies for participants who died or can no longer answer questions about their health or functioning .

Lab Substudy. The Lab Substudy will be conducted after the end of participant follow-up to identify factors associated with cognitive resilience and mechanisms that explain any differential responses to ILI on cognitive function and cognitive impairment. It will be based on stored bio-specimens collected at Look AHEAD baseline, year 10, and during the Look AHEAD Extension: no additional specimen collection is required. Assays will be conducted to determine plasma/serum levels of analytes related to angiogenesis (leptin, apelin, VEGF), inflammation (IL-6, CRP, adiponectin), and sex hormones (testosterone, estradiol).

1.4.4 Schedule for Ascertaining Outcomes

Study measures will be obtained during the Look AHEAD Extension at clinic exams and at six month phone contacts. Participants will be invited to attend two clinic examinations at an interval of approximately two years. All clinic visits will involve a blood draw, physical and anthropometric measures, physical function measures, questionnaires, and interviews for study outcomes. In addition, the second clinic visit will include waist circumference measures and the cognitive assessment among participants who consent. Some participants will also be asked to participate in the DXA and/or accelerometry sub-study. All participants will receive six month phone calls for study outcomes. The list of study measures and frequency of collection is shown in Table 1.

1.4.5 Table 1. Study Measures and Time Points for Data Collection in the Look AHEAD Extension

Table 1. Study measures and time points for data collection in the Look AHEAD Extension			
	EXAM 1 (2016- 2018)	EXAM 2 (2018- 2020)	SIX MONTH PHONE CALLS
Laboratory Measures			
HbA1c	X	X	
Serum Creatinine	X	X	
Stored Plasma, Serum and Whole Blood	X	X	
Physical Measures			
Seated BP & Pulse	X	X	
Weight, Height	X	X	
Waist Circumference		X	
Foot exam for neuropathy	X	X	
Outcomes/Events Interview			
Hospitalizations (& discharge summaries)	X	X	X
Outpatient Visits	X	X	X
Major Health Events	X	X	X
Falls	X	X	X
Renal Replacement Therapy	X	X	X
Amputations	X	X	X
Mortality (death certificates and other records)	X	X	X
Questionnaires			
Participant Contact Form & Proxy Identification	X	X	X
Michigan Neuropathy Screening Instrument	X	X	
Medications	X	X	
SF-36	X	X	
PHQ-9	X	X	
EuroQual (Feeling) Thermometer	X	X	
Loneliness Questionnaire	X		
Paffenbarger Physical Activity	X	X	
Falls Efficacy Scale International	X	X	
Resilience Questionnaire	X		
Pittsburgh Fatigability Scale	X		
Pepper Assessment Tool for Disability (PAT-D)	X	X	
Physical Function and Abilities Questionnaire	X	X	
Sleep Questionnaire	X	X	
Cognitive Function Battery			
Interviewer Administered Battery (45 min)		X	
Digit Symbol Coding Test		X	
Rey Auditory Verbal Learning Test		X	
Modified MiniMental State Exam		X	

Trails Making Test Parts A&B		X	
Modified Stroop Color-Word Test		X	
Functional Assessment Questionnaire (as needed)		X	
Dementia Questionnaire (as needed)		X	
Physical Function			
400-m Walk/alternate 4 meter walk	X	X	
Grip Strength	X	X	
Short Physical Performance Battery (SPPB)	X	X	
Sub studies			
DXA (selected sites)	X		
Accelerometry (selected sites)	X		

